6.5.4.3 Anti-pegcetacoplan peptide antibody and anti-PEG antibody assessments

Patients will have anti-pegcetacoplan peptide Ab and anti-PEG Ab samples collected as outlined in the schedule of assessments (Table 1 and Table 2). The proposed ADA sampling schedule was established to capture the ADA signal at Baseline, any potential early onset and the dynamic profile (transient or persistent) of Ab formation while minimizing pegcetacoplan level in the sample.

Patients who are confirmed as having positive results for anti-pegcetacoplan peptide or anti-PEG Ab in the last dosed sample will be followed up with ADA samples being collected every 6 months until the Ab levels return to baseline. Specific Ab titers will be determined in all samples that are confirmed positive for anti-pegcetacoplan peptide or anti-PEG Ab. Any samples that are confirmed positive for anti-pegcetacoplan peptide Ab will be further characterized with a neutralizing Ab assay.

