### 7.6.5 Immunogenicity data

Frequency tables will be presented to summarize the presence of anti-drug antibodies (ADA) to polyethylene glycol and to pegcetacoplan peptide. ADA evaluable patients are defined as:

- For baseline ADA: having at least one evaluable ADA sample at baseline.
- For treatment-emergent ADA and treatment-boosted ADA: having at least one evaluable ADA sample at baseline and at least one evaluable post dose sample.

Baseline ADA prevalence is defined as the number of patients with ADA positive at baseline divided by the number of patients with evaluable ADA at baseline.

Post-baseline ADA incidence is defined as the proportion of patients developing treatment-emergent ADA among those negative for ADA at baseline, or treatment-boosted ADA, among those positive for ADA at baseline.

Treatment-emergent ADA is defined as ADA that are present at a post-dose visit in a patient who had negative ADA at baseline.

Transient treatment-emergent ADA is defined as treatment emergent ADA detected in a single post dose sample (that was not the last assessment) or in more than 1 ADA sample where the first post dose and last ADA positive samples were separated by a period of less than 112 days (16 weeks), irrespective of any negative and positive samples in between. Persistent treatment emergent ADA is defined as more than 1 positive post dose ADA sample  $\geq 112$  days (16 weeks) apart or a positive ADA sample at the last time point with no further results available.

Treatment-emergent ADA can only be defined if baseline ADA result is obtained.

Treatment-boosted ADA is defined as positive ADA at a titer more than 4-fold the baseline titer found in a patient with positive ADA at baseline. Treatment-boosted ADA can only be defined if baseline ADA titer result is obtained.

Testing for neutralizing antibodies will be performed for all samples with positive ADA. Definitions for baseline Nab prevalence, post-baseline Nab incidence, and treatment-emergent Nab are the same as for ADA but with Nab.

A summary table of baseline ADA prevalence, post-baseline ADA incidence, treatment-emergent/boosted ADA, maximum titers for patients with treatment-emergent/boosted ADA,

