time to treatment-emergent/boosted ADA, duration of treatment-emergent ADA, the proportion of patients with transient and persistent treatment-emergent ADA, baseline Nab prevalence, post-baseline Nab incidence, and prevalence of treatment-emergent/boosted Nab will be presented for pegcetacoplan peptide and polyethylene glycol.

Spaghetti plots of individual ADA titers will be presented for pegcetacoplan peptide and polyethylene glycol in semi-logarithmic format. Negative ADA results will be imputed as 0.1 to display on the log-scale.

All immunogenicity data will be presented in a listing.

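### SAP 7.6.5 reuses the ADA definitions for neutralizing antibodies, which are tested only in ADA-positive samples, and does not say how an ADA-negative sample counts

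*SAP*

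**What the plan says.** SAP 7.6.5 makes the NAb assay a follow-on test: "Testing for neutralizing antibodies will be performed for all samples with positive ADA". It then carries the ADA definitions across in one sentence: "Definitions for baseline Nab prevalence, post-baseline Nab incidence, and treatment-emergent Nab are the same as for ADA but with Nab".

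The definitions carried across are these:

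- Baseline prevalence is the number of positive patients "divided by the number of patients with evaluable ADA at baseline".
- For treatment-emergent status: "Treatment-emergent ADA is defined as ADA that are present at a post-dose visit in a patient who had negative ADA at baseline". Also: "Treatment-emergent ADA can only be defined if baseline ADA result is obtained".
- Boosting has its own condition: "Treatment-boosted ADA can only be defined if baseline ADA titer result is obtained".

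The same section uses ADA for antibodies to both PEG and the pegcetacoplan peptide. Its summary table includes NAb rows for both: "prevalence of treatment-emergent/boosted Nab will be presented for pegcetacoplan peptide and polyethylene glycol".

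Protocol 6.5.4.3 describes the testing differently: "Any samples that are confirmed positive for anti-pegcetacoplan peptide Ab will be further characterized with a neutralizing Ab assay". It says nothing about a neutralizing assay for anti-PEG-positive samples. The titers it describes are those of the anti-peptide and anti-PEG antibodies, not of NAb.

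Immunogenicity is a listed safety endpoint (SAP 3.4), and SAP 1.1 keeps the safety summaries in scope after enrollment was stopped.

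**The concern.** The ADA definitions work for ADA because every scheduled sample can give a positive or a negative result. NAb is different: an ADA-negative sample is not tested, so it has no NAb result. Putting NAb in place of ADA makes the baseline NAb result a condition for entering the calculation, and most patients may not have one.

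At stake is whether the table answers the question a reader will put to it: how many patients had neutralizing antibodies before treatment, and how many developed them on drug. The patients at risk of exclusion are those with a clean baseline, in whom a new NAb is most clearly treatment-related. The PEG rows and the boosted-NAb row raise a further question: what data would fill them.

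**Working it through.** The documents state no NAb rate, denominator or precision, so there is no plan figure to reproduce. The check compares two readings of the definitions and then applies counts.

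**Which reading the SAP's defaults favour.** SAP 5.1 bases percentages on non-missing observations unless stated otherwise. SAP 5.2.2 does not impute missing values unless the SAP or the dataset specifications say so. SAP 9.2.5.2 uses as denominator the patients who have an observation. Where the SAP wants an untested or negative result coded, it says so: a missing Week 24 marker counts as not normalized (7.3.3), and a negative ADA result is plotted as 0.1 (7.6.5). No such rule exists for NAb.

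**Notation.** N = patients with an evaluable baseline ADA result; b = those ADA-positive at baseline; m = those of the b who are NAb-positive at baseline; t1 = baseline ADA-negative patients who become NAb-positive on drug; t2 = patients ADA-positive and NAb-negative at baseline who become NAb-positive.

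**Formulas.**

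- Baseline NAb prevalence: literal m/b; with ADA-negative counted as NAb-negative, m/N. Their ratio is N/b, that is, 1 divided by the baseline ADA prevalence.
- Treatment-emergent NAb: literal t2/(b − m); with the coding rule, (t1 + t2)/(N − m). The literal denominator is at most b − m, because a post-dose NAb result also needs an ADA-positive post-dose sample. The literal reading drops all t1 cases and leaves N − b patients unclassified.

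**Inputs.** N = 38 is the planned pegcetacoplan arm (57 × 2/3, SAP 2.2 and 2.3). Enrollment stopped early, so the real number may be smaller. All ADA and NAb counts are assumptions.

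Baseline prevalence, N = 38:

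| b | m | b/N | Literal m/b | Coded m/N | Ratio N/b |
|---|---|---|---|---|---|
| 2 | 1 | 5.3% | 50.0% | 2.6% | 19.0 |
| 4 | 1 | 10.5% | 25.0% | 2.6% | 9.5 |
| 8 | 2 | 21.1% | 25.0% | 5.3% | 4.8 |

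Treatment-emergent NAb, N = 38:

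| b | m | t1 | t2 | Literal | Coded | New cases lost |
|---|---|---|---|---|---|---|
| 4 | 1 | 3 | 0 | 0/3 | 3/37 = 8.1% | 3 of 3 |
| 4 | 1 | 3 | 1 | 1/3 | 4/37 = 10.8% | 3 of 4 |
| 8 | 2 | 3 | 1 | 1/6 | 4/36 = 11.1% | 3 of 4 |
| 0 | 0 | 3 | 0 | 0/0 | 3/38 = 7.9% | 3 of 3 |

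With b = 4, the literal reading leaves 38 − 4 = 34 of 38 patients unclassified. The literal count is too low whenever t1 is above zero. The literal percentage can err either way: 1/3 is above 10.8%, and 0/3 is below 8.1%.

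**PEG and boosted rows, side by side.** The SAP tests all ADA-positive samples, where ADA includes anti-PEG, and tabulates NAb for PEG. The protocol describes the assay for anti-peptide-positive samples. SAP 11.1 gives the SAP precedence, which settles the analysis text but does not show that an anti-PEG NAb assay was set up. Boosting requires a baseline titer. Boosted NAb is not among the three terms that the carry-over sentence names, and no NAb titer is described.

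**The case against.** The strongest reply is that the literal reading is not the only one. The SAP never defines a NAb-evaluable patient, and the separate definition of ADA-evaluable patients is not among the terms carried over. Where a test is run only on screen-positive samples, counting a screen-negative sample as negative is natural, and a programmer may well do so. The dataset and table specifications, which SAP 10.1 says follow the SAP, could contain the rule. This stands in part: both denominator problems disappear once the rule is stated. But the SAP does not state it, and its own defaults point the other way.

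Three stronger readings are tempting, and the documents do not support them:

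- A reader might infer that everyone who turns NAb-positive on drug drops out. Patients who were ADA-positive and NAb-negative at baseline have a baseline NAb result and stay in.
- A reader might infer that the PEG rows have no assay behind them. The protocol sentence describes anti-peptide testing without restricting NAb testing to it, and the SAP says that all ADA-positive samples are tested. This is a contradiction to reconcile. Deleting the rows outright could discard real results.
- A reader might infer that new NAb would vanish from the report. SAP 7.6.5 lists all immunogenicity data and tabulates ADA incidence separately, so the individual results remain visible.

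**Conclusion.** The point holds for the two denominators. As written, baseline NAb prevalence becomes the proportion of NAb-positive patients among the baseline ADA-positive ones, inflated about 5 to 19 times for an assumed baseline ADA prevalence of about 20% to 5%. Treatment-emergent NAb loses every new case in a patient who was ADA-negative at baseline. How many cases that is cannot be known from the documents.

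The PEG rows are an unreconciled difference between protocol and SAP, and boosted NAb lacks the titer that its definition requires.

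The conclusion rests on following the SAP text and its default rules; an unseen specification could already close the gap. The effect is confined to descriptive safety output. No efficacy test, type I error or sample size is touched. It should be corrected because the fix is nearly free and the table remains in scope.

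**What to change.** Replace the carry-over sentence in SAP 7.6.5 with explicit rules:

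1. A sample negative for the relevant ADA counts as NAb-negative.
2. Baseline NAb prevalence uses as denominator all patients with an evaluable baseline ADA result.
3. Treatment-emergent NAb uses as denominator patients who are NAb-negative at baseline, including those ADA-negative at baseline, with at least one evaluable post-dose ADA sample.
4. Boosted NAb is dropped unless NAb titers are measured; if they are, define it. Post-baseline NAb incidence follows the same choice, because the ADA version includes boosting.
5. NAb rows are limited to anti-pegcetacoplan peptide unless an anti-PEG NAb assay is documented. Align the SAP testing sentence with protocol 6.5.4.3 accordingly.

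The proportion of NAb-positive patients among ADA-positive ones can be shown as an extra row, labelled as such.

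The cost is a few sentences in the SAP and one derivation rule, with no new samples or assays. Before any PEG row is removed, the sponsor should confirm with the bioanalytical laboratory whether anti-PEG-positive samples were tested for NAb.

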## 7.7 EXPLORATORY ENDPOINT ANALYSIS

The exploratory endpoints will be summarized with numerical descriptive statistics.

- Pegcetacoplan concentrations at Week 24 and Week 48.
- Changes from Baseline to Week 24 and Week 48 in complement biomarkers (C3 levels, functional assays for classical and alternative complement pathways).
- Changes from Baseline through Week 24 and Week 48 in C3 deposition on RBCs by flow cytometry.
- Changes from Baseline to Week 24 and Week 48 in inflammatory biomarkers: TNF $\alpha$ , IL-6, IL-10, IFN $\gamma$  and IL-1 $\beta$ .
- Normalization of haptoglobin level at Week 24, Week 48 and Week 96
- Time to first normalization from Baseline to Week 24 for haptoglobin level

The following endpoint will be summarized with frequencies via counts and percentages.

- Normalization of haptoglobin level at Week 24, Week 48 and Week 96.

The following endpoint will be summarized with survival estimates in a table.

- Time to first normalization from Baseline to Week 24 for haptoglobin level.

## 7.8 PHARMACOKINETIC AND PHARMACODYNAMIC ENDPOINT ANALYSIS

PK/PD analyses will be described in the PK/PD Analysis Plan. All population modelling will be described and done in the PK/PD plan. Selected PK/PD summaries included in this analysis are described in this section.

### 7.8.1 PK Summaries

Pegcetacoplan concentration time results will be evaluated using the PK set. Concentrations will be summarized, using descriptive statistics, over time, in the randomized treatment groups. Individual patient concentration-time data will be plotted against actual sampling time. Individual patient concentration time data will also be plotted with patients who are positive for ADA are indicated with a different color. Median profiles of the concentration-time data, using nominal sampling times, will also be presented. Both linear-linear and linear-log plots will be presented.

Concentrations below the lower limit of quantification (LLOQ) will be replaced with LLOQ, except for <LLOQ pre-treatment concentrations, which will be replaced with zero.

### 7.8.2 PD Summaries

The PD endpoints will be evaluated using the PD set. Absolute values, changes from Baseline and percentage changes from Baseline will be summarized using descriptive statistics, over time by treatment group. Individual patient time profiles will be plotted against actual sampling time. Median profiles, over time, using nominal sampling time, will also be presented.

The PD endpoints in each treatment group will be compared using mixed effect repeated measures analyses.

- Changes from Baseline to Week 24 and Week 48 in complement biomarkers (C3 levels, functional assays for classical and alternative complement pathways).
- Changes from Baseline through Week 24 and Week 48 in C3 deposition on RBCs by flow cytometry.
- Changes from Baseline to Week 24 and Week 48 in inflammatory biomarkers: TNF $\alpha$ , IL-6, IL-10, IFN $\gamma$  and IL-1 $\beta$ .

## 8 INTERIM ANALYSIS

No formal interim analyses are planned for the primary endpoint. Data will be reported for Part A (double-blind treatment period) once all patients have completed their Week 24 visits (or have early discontinued) and the database has been cleaned and verified for all visits up to and including Week 24. Similarly, data will be reported after Part B.

## 9 SOFTWARE AND PROGRAMMING SPECIFICATIONS

All datasets, TLFs, and statistical analyses will be generated using SAS, Release 9.4 or higher (SAS Institute Inc., Cary, NC, USA). Computer-generated datasets, table, listing and figure output will adhere to the following specifications:

### 9.1 GENERAL PROGRAMMING SPECIFICATIONS

- One SAS program can create several outputs, or a separate SAS program can be created for each output at the statistical programmer's discretion.
- Each output will be stored in a separate file.
- Output files will be delivered in Word format / rtf format.
- Numbering of TLFs will follow ICH E3 guidance

### 9.2 TABLE, LISTING, AND FIGURE FORMAT

#### 9.2.1 General

- All TLFs will be produced in landscape format, unless otherwise specified.
- All TLFs will be produced using the Courier New font, size 8.

- The data displays for all TLFs will have a 1.5-inch binding margin on top of a landscape-orientated page and a minimum 1-inch margin on the other 3 sides.
- Headers and footers for figures will be in Courier New font, size 8.
- Legends will be used for all figures with more than 1 variable, group, or item displayed.
- TLFs will be in black and white (no color), unless otherwise specified.
- Specialized text styles, such as bolding, italics, borders, shading, and superscripted and subscripted text, will not be used in the TLFs, unless otherwise specified. On some occasions, superscripts 1, 2, or 3 may be used (e.g.,  $m^2$ ,  $C_{max}$ ).
- Only standard keyboard characters will be used in the TLFs. Special characters, such as non-printable control characters, printer-specific, or font-specific characters, will not be used. Hexadecimal-derived characters will be used, where possible, if they are appropriate to help display math symbols (e.g.,  $\mu$ ). Certain subscripts and superscripts (e.g.,  $cm^2$ ,  $C_{max}$ ) will be employed on a case-by-case basis.
- Mixed case will be used for all titles, footnotes, column headers, and programmer-supplied formats, as appropriate.

### 9.2.2 Headers

- All outputs should have the following header at the top left of each page:

Sobi  
Protocol: Sobi.PEGCET-101

- All outputs should have Page n of N at the top or bottom right corner of each page. TLFs should be internally paginated in relation to the total length (i.e., the page number should appear sequentially as page n of N, where N is the total number of pages in the table).
- The date (date output was generated) should appear along with program name and location as the last footer on each page.

### 9.2.3 Display Titles

Each TLF should be identified by the designation and a numeral. (e.g., Table 14.1.1). ICH E3 recommended numbering will be used. A decimal system (x.y and x.y.z) should be used to identify TLFs with related contents. The title is centered. The analysis set should be identified on the line immediately following the title. The title and table designation are single spaced. A solid line spanning the margins will separate the display titles from the column headers. There will be 1 blank line between the last title and the solid line.

Table x.y.z  
First Line of Title  
Second Line of Title (if needed)  
Analysis Set

#### 9.2.4 Column headers

- Column headings should be displayed immediately below the solid line described above in initial upper-case characters.
- For numeric variables, include “unit” in column or row heading when appropriate.
- Analysis set sizes will be presented for each treatment group in the column heading as (N=xx) (or in the row headings if applicable). This is distinct from the ‘n’ used for the descriptive statistics representing the number of patients in the analysis set.

#### 9.2.5 Body of the data display

##### 9.2.5.1 *General conventions*

Data in columns of a table or listing should be formatted as follows:

- alphanumeric values are left-justified;
- whole numbers (e.g., counts) are right-justified; and
- numbers containing fractional portions are decimal aligned.

##### 9.2.5.2 *Table conventions*

- Units will be included where available
- If the categories of a parameter are ordered, then all categories between the maximum and minimum category should be presented in the table, even if n=0 for all treatment groups in a given category that is between the minimum and maximum level for that parameter. For example, the frequency distribution for symptom severity would appear as:

Severity Rating	N
very severe	2
severe	0
moderate	8
mild	3

Where percentages are presented in these tables, zero percentages will not be presented and so any counts of 0 will be presented as 0 and not as 0 (0%).

- If the categories are not ordered (e.g., Medical History, Reasons for Discontinuation from the Study, etc.), then only those categories for which there is at least 1 patient represented in 1 or more groups should be included.
- An Unknown or Missing category should be added to any parameter for which information is not available for 1 or more patients.
- Unless otherwise specified, the estimated mean and median for a set of values should be presented to 1 more significant digit than the original values, and standard deviations should be presented to 2 more significant digits than the original values. The minimum and maximum

should report the same significant digits as the original values. For example, for systolic blood pressure:

N	XX
Mean	XXX.X
Std Dev	X.XX
Median	XXX.X
Minimum	XXX
Maximum	XXX

- P-values should be output in the format: “0.xxx”, where xxx is the value rounded to 3 decimal places. Any p-value less than 0.001 will be presented as < 0.001. If the p-value should be less than 0.0001 then present as < 0.0001. If the p-value is returned as > 0.999 then present as > 0.999
- Percentage values should be printed to 1 decimal place, in parentheses with no spaces, 1 space after the count (e.g., 7 [12.8%], 13 [5.4%]). Values that round down to 0.0 will be displayed as ‘< 0.1’. Unless otherwise noted, for all percentages, the number of patients in the analysis set for the treatment group who have an observation will be the denominator. Percentages after zero counts should not be displayed and percentages equating to 100 % should be presented as 100 %.
- Unless otherwise specified, tabular display of data for medical history, prior / concomitant medications, and all tabular displays of adverse event data should be presented by the body system, drug class, or SOC in descending order, assuming all terms are coded. Within the body system, drug class and SOC, medical history (by preferred term), drugs (by ATC code), and adverse events (by preferred term) should be displayed in decreasing order. If incidence for more than 1 term is identical, they should then be sorted alphabetically.
- The percentage of patients is normally calculated as a proportion of the number of patients assessed in the relevant treatment group (or overall) for the analysis set presented. However, careful consideration is required in many instances due to the complicated nature of selecting the denominator, usually the appropriate number of patients exposed. Details of this will be provided in footnotes in tables where appropriate.
- For categorical summaries (number and percentage of patients) where a patient can be included in more than 1 category, a footnote will note if the patient should be included in the summary statistics for all relevant categories or just 1 category and the criteria for selecting the criteria.
- Where a category with a subheading (such as system organ class) has to be split over more than 1 page, output the subheading followed by “(cont)” at the top of each subsequent page. The overall summary statistics for the subheading will only be output on the first relevant page.

#### **9.2.5.3 Listing conventions**

- Listings will be sorted for presentation in order of treatment groups (as above), subject ID visit/collection day, and visit/collection time.
- Dates will be printed in SAS® DATE9.format (“DDMMYY YYYY”: 01JUL2000). Missing portions of dates will be represented on patient listings as dashes (--JUL2000). Dates that are

missing because they are not applicable for the patient are output as “N/A”, unless otherwise specified.

- All observed time values will be presented using a 24-hour clock HH:MM or HH:MM:SS format (e.g., 11:26:45, or 11:26). Time will only be reported if it was measured as part of the study.
- Units will be included where available

